9.6. Safety Analyses

All safety analyses will be performed using the Safety population (see [Section 9.1.2](#)). No formal statistical comparisons between these two treatment arms are planned.

9.6.1. Adverse Events

Adverse event terms recorded on the CRFs will be mapped to preferred terms using the Medical Dictionary for Regulatory Activities (MedDRA). The Investigator will classify the severity of AEs using CTCAE v5 and will judge each event to be “not related” or “related” to study treatment.

A treatment emergent adverse event (TEAE) is defined as any event that begins or worsens on or after the date of first dose of study treatment. Only TEAEs with an onset date prior to date of decision for treatment discontinuation (defined as the later of the date of the decision to permanently discontinue study treatment or the date of the last dose of study treatment) + 30 days (+ 100 days for SAEs and certain other AEs; [Section 8.3](#)) will be tabulated in summary tables.

The frequency and percentage of subjects with TEAEs will be tabulated for overall incidence by system organ class and/or preferred term by treatment arm. Related TEAEs, serious TEAEs, related serious TEAEs, high-grade TEAEs, Grade 5 TEAEs, and TEAEs resulting in study treatment discontinuation will be similarly summarized. Summaries by worst reported severity for each event within a subject will also be provided.

At each level of summarization, a subject will be counted only once for each AE preferred term he/she experiences within that level (ie, multiple episodes of events with the same preferred terms will be counted only once).

All reported subject deaths will be summarized by treatment group, cause of death, and relationship to study treatment.

9.6.2. Laboratory Test Results

Laboratory test results will be summarized by treatment group to evaluate worst post-baseline CTCAE grade and shifts or changes from baseline.

9.6.3. Other Safety Endpoints

Changes or shifts from baseline in vital signs, ECOG performance status, and QTc interval will be summarized by treatment group.

The number of subjects experiencing dose reduction, interruption/delay, and/or discontinuation due to an AE will be provided.

Concomitant medications will be standardized using the World Health Organization drug dictionary and summarized by class and preferred term.

9.7. Power and Sample Size

The study is designed to provide adequate power for analyses of both primary endpoints of PFS and OS comparing the experimental arm (cabozantinib + atezolizumab) with the control arm (sorafenib), and for the analysis of the secondary endpoint of PFS comparing single-agent cabozantinib with control arm. For the primary endpoints, a larger sample size is needed to provide reasonable power for OS than is required to evaluate PFS. As a result, if PFS were to be evaluated in the entire study sample, the PFS events may be biased toward shorter progression times. Thus, to allow longer, more robust PFS follow up among a smaller number of subjects, this study employs a “trial within a trial design” (Hessel et al 2016).

The total sample size was planned to be 740 subjects randomized in a 2:1:1 fashion: 370 to the experimental combination arm (cabozantinib + atezolizumab), 185 to the control arm (sorafenib),

and 185 to the single-agent cabozantinib arm. However, enrollment commenced under a randomization ratio of 6:3:1 per the original protocol design, and there was a dynamic transition in randomization allocation over time. As a result, the needed enrollment of 185 subjects in the single-agent cabozantinib arm was not expected to be reached at the planned total global enrollment phase sample size of 740 subjects. Therefore, to ensure complete enrollment in the single-agent cabozantinib arm, the total global enrollment phase was extended to accrue a total of approximately 840 subjects.

For primary PFS, a total of 257 events in the first 372 subjects randomized in a 2:1 ratio in the experimental and control arms (n=248 and 124, respectively; the PITT population) provide the study with 90% power for a 2-sided log-rank test with a 1% level of significance to detect a hypothesized true HR of 0.6. Assuming an exponential distribution of PFS, this corresponds with a 67% increase in median PFS from 3.6 months to 6.0 months. The minimum observed effect that would result in statistical significance for PFS is an HR of 0.71, a 41% improvement in median from 3.6 to 5.1 months. Interim analysis of the primary PFS endpoint is not planned.

For OS, a total of 368 deaths among all 555 subjects randomized in a 2:1 ratio in the experimental (n=370) and control arms (n=185) are required to provide 90% power to detect an HR of 0.69 using the log-rank test and a 2-sided significance level of 4%. Assuming an exponential distribution for OS, this corresponds to a 45% increase in median survival from 12.3 months to 17.8 months. The minimum observed effect that would result in statistical significance for the primary analysis of OS is an HR of 0.7942, a 26% improvement in median from 12.3 to 15.5 months.

For the secondary endpoint of PFS for the single-agent cabozantinib arm vs the control arm (sorafenib), a total of 283 events among all 370 subjects (185 per arm) in the single-agent cabozantinib and control arms provides the study with 85% power for a 2-sided log-rank test with a 1% level of significance to detect a hypothesized true HR of 0.65. Assuming an exponential distribution for PFS, this corresponds with a 53% increase in median PFS from 3.6 months to 5.5 months. The minimum observed effect that would result in statistical significance for PFS is an HR of 0.735, a 36% improvement in median from 3.6 to 4.9 months.

With an average accrual rate of 30 subjects per month it is estimated that it will take approximately 18.4 months to observe the required primary PFS events (16.5 months of subject accrual) and approximately 38 months to observe the required deaths for OS (25 months of subject accrual) to evaluate the primary endpoints in the combination and control arms.

Assuming the same accrual rate, it is anticipated that it will take approximately 25 months to

observe the required secondary PFS events (25 months of subject accrual) to evaluate the secondary endpoint in the single-agent cabozantinib and control arms. The true intervals required to meet these milestones may be longer or shorter due to divergence from assumptions, including non-constant accrual rate due to the time required for all study sites to become active, or due to the impact of the global COVID-19 pandemic on subject enrollment and other aspects of study conduct. The sample size for the global study may be increased up to an additional 25% if a review of the accumulating data suggests that the COVID-19 pandemic has caused the rate of study dropout or non-compliance to increase to a degree that the ability to adequately evaluate study endpoints may be undermined. The Mainland China Extension Phase will not be expanded beyond 148 subjects.

An overview of the primary and secondary endpoints and operating characteristics is shown in [Table 33](#):

Table 33: Summary of Endpoint Operating Characteristics

Accrual per month	30 subjects		
Randomization allocation	2:1 within Experimental and Control Arms		1:1 within Single-Agent Cabozantinib and Control Arms
Endpoint:	PFS: Primary endpoint	OS: Primary endpoint	PFS: Secondary endpoint
Power	90%	90%	85%
Alpha allocated (2-sided)	0.01	0.04	0.01
# of interim analyses (approximate information fraction)	0 (NA)	2 (33%, 66%) ^a	1 (67%)
Assumed median, control (months)	3.6	12.3	3.6
Assumed median, experimental (months)	6.0	17.8	5.5
Assumed HR	0.60	0.69	0.65
Number of events	257	368	283
N for analysis	372	555	370
Population n1 vs n2	PITT Population 248 vs 124	ITT Population 370 vs 185	ITT Population 185 vs 185
Time to enroll (months)	16.5	25	25
Time to trigger event (months)	18.4	38	25

^a Should the timing of the first interim analysis trend towards an information fraction much higher than expected (eg, due to faster-than-expected deaths or slower-than-expected PFS events), the plan for the interim analyses of OS may be modified (see [Section 9.8](#)).

China Subpopulation Sample Size: Up to 148 subjects from mainland China are planned to be enrolled (in the global and Mainland China Extension phases) in the study to meet a target of approximately 20% of the total sample size in the global enrollment (N=740). This population size is expected to be sufficient to allow evaluation of consistency in efficacy and safety in the China subpopulation compared with the global study per NMPA guidance. Analyses for the China subpopulation are described in [Section 9.9](#).

9.8. Interim Analyses

The number of events required to evaluate OS is based upon assumptions currently available and provides high power to detect the smallest clinically meaningful difference in OS under these assumptions. However, as there is uncertainty in the assumptions, interim analyses provide an opportunity to stop the trial early if the treatment benefit of the experimental arm is larger than expected, potentially allowing the new regimen to become available sooner to this patient population.

Two interim analyses of OS are planned at approximately the 33% and 66% information fractions based on a total alpha of 4%. However, if the null hypotheses are rejected for both the primary and secondary PFS endpoints, the 1% alpha for PFS will be reallocated to OS per the fallback method. As a consequence, the final OS analysis will employ critical values from the spending function at the 5% level. The alpha level of the interim analysis at 66% will be dependent on the timing of the interim analysis and the results of secondary PFS interim and final analyses. The second interim analysis of OS at 66% information fraction can be conducted at the overall 5% alpha level only if it occurs after the null hypothesis for the secondary PFS is rejected at the interim analysis.

Details and boundaries for these interim and the final analyses are shown in the table below:

	Critical Values for Testing OS					
	4.0%		4.96%		5.0% ^a	
OS alpha total	Critical p-value	HR to reject	Critical p-value	HR to reject	Critical p-value	HR to reject
33% ^b	≤ 0.00011	≤ 0.478	NA ^c	NA ^c	≤ 0.0021	≤ 0.482
66% ^d	≤ 0.00867	≤ 0.701	≤ 0.01196	≤ 0.705	≤ 0.0120	≤ 0.705
100%	≤ 0.03728	≤ 0.794	≤ 0.04588	≤ 0.797	≤ 0.0463	≤ 0.797

HR, hazard ratio; NA, not applicable; OS, overall survival.

^a Analyses of OS will be conducted at 5% alpha level only if the null hypotheses for both the primary and secondary PFS endpoints are rejected prior to testing OS.

^b OS will not be tested at the 33% information fraction unless the null hypothesis for PFS has been rejected.

^c The interim analysis at 33% information fraction will be conducted at 4% alpha level.

^d The interim analysis at 66% information fraction will be conducted at 4% alpha level if it occurs prior to the secondary PFS analysis. It will be conducted at 4.96% alpha level if it happens after the null hypothesis for secondary PFS is rejected at the time of final analysis. It will be conducted at 5% alpha level only if the null hypothesis for secondary PFS is rejected at the interim analysis.

Rejection of the null hypotheses for OS at the first interim analysis at about 33% information is not expected: it is designed primarily as an administrative analysis, expected to coincide with the primary analysis of PFS, and will be performed only if the null hypothesis for PFS is rejected.

Should the timing of the first interim analysis (IA1) of OS trend towards an information fraction much higher than expected (eg, due to faster-than-expected deaths or slower-than-expected PFS events), the interim analyses of OS will be conducted as follows:

OS IA1 IF	Proceed as	Rationale
< 50%	perform IA1 and IA2 as planned above	similar conditions to original plan
50 to < 66%	
 perform IA1 at time of primary PFS, irrespective of whether PFS null hypothesis is rejected or not Conduct IA2 at 80% IF (instead of 66%) 	
 Higher than expected information for OS negates administrative nature of the analysis. Preserves two interim analyses as planned with reasonable intervals between them
≥ 66%	perform a single interim analysis at 66% IF, irrespective of timing or results of primary PFS analysis.	Information fraction meets or exceeds that of planned analysis at 66%

IA1, first interim analysis; IA2, second interim analysis; IF, information fraction; OS, overall survival

An interim analysis of secondary PFS is planned contemporaneously with the primary PFS analysis and will be conducted only if the null hypothesis for primary PFS is rejected. It is anticipated to be at approximately 67% information fraction based on a total alpha of 1%. At this fraction, the critical p-value is 0.0096, and the maximum HR to reject the null hypothesis is 0.626.

Due to logistical considerations in event ascertainment and operational planning and conduct, the actual analyses may include more or fewer events than the target information fractions. The actual critical values employed at the interim and final analyses of secondary PFS and OS will depend upon the actual information fraction at the time of the analyses. Descriptive supportive analyses will be provided at the planned information fraction at the time of the analyses.

If a null hypothesis is rejected for a given endpoint at interim analysis (secondary PFS or OS), no subsequent testing of that endpoint will be performed.

Interim analysis of primary PFS and futility analyses of PFS or OS are not planned.

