9.2.2.2. Overall Survival

The primary analysis of OS is event-driven and will be conducted after at least 368 deaths have been observed in the ITT population ([Section 9.1.1](#)) for the experimental and control arms.

Hypothesis testing between the two treatment arms will be performed using the stratified log-rank test with a 2-sided α level of significance (the α level will be defined per [Section 9.5](#)). The stratification factors will be the same as those used to stratify the randomization.

The median duration of OS and the associated 95% and 1- α % CI for each treatment arm will be estimated using the Kaplan-Meier method. The HR with 95% and 1- α % CIs will be estimated using a Cox regression model and will include the same stratification factors described above.

Details of interim analyses of OS are provided in [Section 9.8](#).

At any analysis of OS (interim or primary), if the p-value for the stratified log-rank test is statistically significant and the HR ($\lambda_{\text{cabozantinib + atezolizumab}} / \lambda_{\text{sorafenib}}$) is < 1 , the null hypothesis of no difference in OS between the two treatment arms will be rejected and it will be inferred that OS is superior in the group receiving cabozantinib + atezolizumab compared with the group receiving sorafenib.

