9.5. Control of Type I Error

Inflation of Type 1 error associated with testing of multiple primary endpoints and a secondary efficacy endpoint (PFS between single-agent cabozantinib and control) will be controlled by a modified Bonferroni procedure, a gatekeeping technique, and the fallback method (FDA 2017). Initially, the study-wise 2-sided alpha of 5% will be unequally allocated between primary endpoints PFS (1%) and OS (4%). The secondary PFS endpoint will be tested at the 1% level only if the primary PFS test is successful. If the null hypotheses are rejected for both the primary and secondary PFS endpoints, the 1% alpha for PFS will be reallocated to OS, allowing it to be tested at the 5% level.

Two interim analyses of OS are planned at the 33% and 66% information fractions (the first interim will coincide with the primary analysis of PFS and will be performed only if the null hypothesis for PFS is rejected and is expected to occur at approximately the 33% information fraction). One interim analysis is planned for secondary PFS endpoint contemporaneous with the primary PFS analysis with anticipated information fraction of 67%. Type 1 error associated with interim analyses will be controlled using Lan-DeMets O'Brien-Fleming (LD-OF) alpha-spending functions based upon a 4% total alpha allocation for OS and 1% for secondary PFS.

The testing and alpha reallocation are elucidated below.

First, test primary PFS at the 1% level. Then:

1. If primary PFS is significant:
 - a. Re-allocate its 1% alpha to secondary PFS per the fallback method.
 - b. Conduct interim analysis of OS at 33% per LD-OF with 4% total alpha
 - c. Conduct interim analysis of secondary PFS endpoint at 67% per LD-OF with 1% alpha.
 - i. If interim analysis of secondary PFS is significant:
 - Re-allocate its 1% alpha to OS
 - Conduct interim analysis of OS at 66% per LD-OF with 5% alpha
 - No further inferential testing of secondary PFS will be performed.

- ii. If interim analysis of secondary PFS is not significant:
 - The final analysis of secondary PFS will be conducted at an alpha of 0.0096.
 - The alpha of subsequent OS analyses will be dependent on the timing and result of the final secondary PFS analysis.

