 - The second interim analysis and the final for OS will be conducted per LD-OF with 4% alpha, if the second interim analysis occurs prior to the final analysis for secondary PFS, or, if it occurs after the final secondary PFS analysis where the final secondary PFS fails to reject its null hypothesis.
 - The subsequent OS analyses will be conducted per LD-OF with 4.96% alpha if it occurs after the rejection of the null hypothesis for secondary PFS.
- d. Conduct interim and final analyses of OS with appropriate alpha as determined above

2. If primary PFS is not significant:

- a. Secondary PFS analysis cannot be conducted
- b. Conduct interim and final analyses of OS per LD-OF with 4% total alpha
 - i. If OS is not significant at final analysis, procedure ends

All other statistical evaluations of efficacy will be considered exploratory.

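### OS boundary table: the hazard ratios in the 4.96% and 5% columns do not match their p-values at 368 deaths, one p-value is misprinted tenfold, and 4.96% and 5% are both given for one branch

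*Protocol*

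**What the plan says.** Protocol 9.7 and SAP 2.3 set the OS analysis at 368 deaths, randomized 2:1, with a two-sided alpha of 4%. Protocol 9.8 then gives three columns of critical p-values and hazard ratios, introduced by "Details and boundaries for these interim and the final analyses are shown in the table below". SAP Table 11 (section 7.3) gives only the 4% and 5% columns.

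| Look | 4% | 4.96% (protocol only) | 5% |
|---|---|---|---|
| 33% | 0.00011 / 0.478 | NA | 0.0021 (SAP: 0.00021) / 0.482 |
| 66% | 0.00867 / 0.701 | 0.01196 / 0.705 | 0.0120 (SAP: 0.01202) / 0.705 |
| 100% | 0.03728 / 0.794 | 0.04588 / 0.797 | 0.0463 (SAP: 0.04626) / 0.797 |

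On the first look, protocol footnote c says "The interim analysis at 33% information fraction will be conducted at 4% alpha level". SAP 4.9 states that Table 11 corrects minor typographical error in the protocol.

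On the reallocated alpha, the first paragraph of protocol 9.5 says that once both PFS hypotheses are rejected "the 1% alpha for PFS will be reallocated to OS, allowing it to be tested at the 5% level", and 9.8 says "the final OS analysis will employ critical values from the spending function at the 5% level". For the branch where secondary PFS is rejected at its final analysis, the step list in 9.5 says "The subsequent OS analyses will be conducted per LD-OF with 4.96% alpha". Footnote d says of the 66% look "It will be conducted at 4.96% alpha level if it happens after the null hypothesis for secondary PFS is rejected" at that final analysis. SAP 7.2 and 7.3 have no 4.96% case.

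**The concern.** Each p-value and the hazard ratio beside it should be the same boundary on two scales. In two of the three columns they are not, so the table gives two different thresholds for a primary endpoint. A reader who uses the HR column would misjudge a result near the boundary.

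The misprinted 0.0021 is ten times the intended value and is the only figure in the OS table that errs in the anti-conservative direction.

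The alpha conflict differs in kind. Critical values will be recalculated at the actual information, but that recalculation needs a total alpha as input, and the documents give two for the same situation. The choice should be fixed before OS is tested.

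**Working it through.** **Inputs.** 368 deaths, 2:1 allocation, looks at about 33%, 66% and 100%, and LD-OF spending (protocol 9.5, 9.7, 9.8; SAP 2.3, 7.3). With *d* deaths at a look and 2:1 allocation, information is *d* × (2/3) × (1/3) = 2*d*/9, so the cut-off is HR = exp(−z / √(2*d*/9)). Here z comes from the two-sided nominal p.

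**Plan's own figure first.** With looks at 123/245/368 deaths, LD-OF at 4% gives p = 0.00011/0.00867/0.03728 and HR = 0.478/0.701/0.794. This is the printed 4% column, and it agrees with the minimum significant HR of 0.7942 in protocol 9.7.

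**Final look.** There is no information fraction to vary here. √(2 × 368/9) = 9.043.

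- 5%: p = 0.04626, z = 1.993, HR = exp(−1.993/9.043) = 0.802.
- 4.96%: p = 0.04588, z = 1.9965, HR = exp(−1.9965/9.043) = 0.802.
- Printed 0.797: z = 0.2269 × 9.043 = 2.052, p = 0.0402, against the paired 0.0463 (0.04588 in the 4.96% column).

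**All looks at 368 deaths.**

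| Column | Looks | Computed p | Computed HR | Printed HR |
|---|---|---|---|---|
| 5% | 1/3, 2/3, 1 | 0.00021/0.01202/0.04626 | 0.491/0.712/0.802 | 0.482/0.705/0.797 |
| 5% | 0.33, 0.66, 1 | 0.00019/0.01153/0.0464 | 0.488/0.709/0.802 | 0.482/0.705/0.797 |
| 5% | 123/245/368 deaths | 0.00021/0.01195/0.04628 | 0.492/0.711/0.802 | 0.482/0.705/0.797 |
| 4.96% | 1/3, 2/3, 1 | 0.00020/0.01189/0.0459 | –/0.711/0.802 | NA/0.705/0.797 |

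The first row reproduces the SAP's 5% p-values to every printed digit, but not its hazard ratios. Running the first look at 4% and then switching to 5% (looks at 0.33 and 0.66) gives 0.709/0.802 at the last two looks, so the switch does not explain the gap.

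**Size.**

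- At 66–67% information, HR 0.705 is p = 0.0102–0.0099, against 0.0120.
- At about 123 deaths, HR 0.482 is p = 0.00014, against 0.00021.
- Used as the decision rule at all three looks, the printed 5% hazard ratios would spend about 4.3% two-sided, not 5%.
- The printed 5% hazard ratios do reproduce with 348 deaths (116/232/348: 0.4815/0.705/0.797). Neither document mentions 348, so a smaller event count is only an inference about the cause.

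**The 0.0021 cell.** At 368/3 = 122.7 deaths, p = 0.0021 corresponds to HR 0.555, not the 0.482 beside it. Used literally, with the 5% boundaries at the later looks, it would give 5.09% two-sided.

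**4.96% versus 5%.** LD-OF at 1% with one look at 67% gives secondary PFS nominal critical p-values of 0.0012 at the interim and 0.0096 at the end. Protocol 9.5 takes the second as an alpha: "The final analysis of secondary PFS will be conducted at an alpha of 0.0096". It then adds it to 4%: 0.04 + 0.0096 = 0.0496. But 0.0096 is the nominal level of one look. The two looks together are a 1% test, and rejection at either releases the full 1%. The choice changes the final OS critical p from 0.04588 to 0.04626. At a true HR of 0.75 it changes power from 73.3% to 73.4%.

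**The case against.** The strongest reply is that little depends on this table. Protocol 9.2.2.2 rejects "if the p-value for the stratified log-rank test is statistically significant" and the HR is below 1; SAP 7.1.2.5 has the same rule. Protocol 9.8, SAP 7.3 and the SAP addendum tie the critical values to the information actually available. The HR error is 0.005 to 0.010, conservative, and confined to the branch where both PFS hypotheses are rejected. All of this stands, and it is why the matter is not a type I error problem.

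The 0.0021 cell is already 0.00021 in the SAP, and footnote c with step 1b of 9.5 keeps the protocol from using it. That also stands. But the protocol text, which already refers to Amendment 3.0, still prints the wrong value.

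The protocol does say when 4.96% is meant to apply, and the SAP is based on Amendment 2.0, so version sequence may explain part of the difference. The conflict nevertheless remains for the final OS test: within the protocol, between the step list and the statements in 9.5 and 9.8 that OS goes to 5%; and between protocol and SAP. Recalculating at the actual information fraction cannot resolve it.

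Replacement interim hazard ratios depend on the event counts assumed. Between the 1/3, 2/3 looks and the 123/245 counts they move by at most 0.001. With exactly 33% and 66% the 5% values are 0.488 and 0.709. No choice tried gives the printed figures, and 0.802 at the final look is the same on all of them. The right response is to state the counts.

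**Conclusion.** The concern holds in all three parts and should be fixed.

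1. At 368 deaths the hazard ratios in the 4.96% and 5% columns are too strict for their p-values: by about 0.005 at the final look, 0.006–0.007 at the second and 0.009 at the first. SAP Table 11 has the same error in its 5% column.
2. The protocol's 0.0021 is a tenfold misprint in a cell that its own sequence does not use.
3. For OS tested after secondary PFS is rejected at its final analysis, the documents give two total alphas. Both are valid; 4.96% is slightly conservative.

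This rests on 2:1 allocation, LD-OF spending and the usual log-rank approximation, which reproduces the 4% column. Family-wise error is not at risk as long as the p-value decides. The practical exposure is a final HR between 0.797 and 0.802, where the two printed criteria disagree.

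**What to change.** - **Protocol 9.8 table.** Change 0.0021 to 0.00021, or mark the 33%/5% cell NA because footnote c runs that look at 4%. Replace the 5% hazard ratios with about 0.491 (or NA)/0.712/0.802. If the 4.96% column is kept, replace its hazard ratios with NA/0.711/0.802.
- **SAP Table 11.** Replace the 5% hazard ratios with 0.491/0.712/0.802, and treat the 33%/5% cell as in the protocol.
- **Both tables.** State the event counts or information fractions used, and check every p-value and HR against that one set.
- **Alpha.** Before OS is tested, name one reallocated alpha for the branch where secondary PFS is rejected at its final analysis. Use it in protocol 9.5, protocol 9.8 with footnote d, and SAP 7.2 and 7.3. 5% is the simpler choice: it is valid and already matches the SAP. If 4.96% is preferred, the SAP needs that case added.

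The cost is table and wording corrections in two documents. No patients, event targets or analysis times change, and the family-wise error stays at or below 5% with either alpha.
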